This is the first study of venetoclax in combination with pomalidomide and dexamethasone. This study will determine if venetoclax and pomalidomide can be safely combined for treatment of subjects with R/R MM and produce potentially meaningful clinical activity.

Clinical Hypothesis

Overall, MM accounts for more than 10% of all hematologic malignancies and 1% of all malignancies. It is the most prevalent hematologic malignancy in patients older than 65 years of age. Approximately 114,000 new cases of MM were diagnosed worldwide in 2012.⁵

The treatment paradigms and outcomes for patients with MM have markedly changed in the past decade with the introduction of several new, more effective, and less toxic therapies, doubling the median OS from 3 years to 6 years.^{6,7} Nevertheless, significant unmet needs remain for the treatment of MM, as this disease has no cure to date and current therapies can only slow disease progression, prolong survival, and minimize symptoms. In fact, the majority of patients with MM will relapse or become refractory, regardless of the line of therapy, which is associated with high morbidity and mortality. Additionally, the remission duration in relapsed myeloma decreases with each regimen.

Various treatment options are available in case of relapse ranging from conventional cytostatic agents such as melphalan or cyclophosphamide and steroids to novel classes of drugs, including IMiDs, proteasome inhibitors (PIs), histone deacetylase (HDAC) inhibitors, and monoclonal antibodies (anti-CS1, anti-CD38) with and without corticosteroids. Most recommended treatment protocols comprise variable combinations of these drugs.

The mechanisms of action of venetoclax (BCL-2 inhibitor) and pomalidomide (IMiD) are independent and have the potential to provide additive clinical benefit relative to the individual agents alone in subjects with R/R MM.

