5.2 Contraception Recommendations

Subjects must follow the contraceptive guidelines as specified below (minimum requirements for venetoclax and pomalidomide; local guidelines and pomalidomide REMS program may differ and should be followed, when applicable).

If female, subject must be either:

- Postmenopausal defined as:
 - age > 55 years with no menses for at least 24 or more consecutive months without an alternative medical cause; or
 - age ≤ 55 years with no menses for 24 or more consecutive months without an alternative medical cause and a follicle-stimulating hormone level > 40 IU/L

or

- Permanently surgically sterile (bilateral oophorectomy, bilateral salpingectomy, or hysterectomy)

or

- Women of childbearing potential must use 2 reliable forms of contraception simultaneously from at least 30 days before initiating treatment with study drugs through at least 30 days after the last dose of any study drug. The 2 methods of reliable contraception must include 1 highly effective method and 1 additional effective (barrier) method. The following are examples of highly effective and additional effective methods of contraception:
 - Highly Effective Methods
 - hormonal (birth control pills, injections, levonorgestrel-releasing intrauterine system, medroxyprogesterone acetate depot injections, ovulation inhibitory progesterone-only pill [e.g., desogestrel])
 - bilateral tubal occlusion/ligation at least 1 month before study Day 1
 - bilateral tubal occlusion via hysteroscopy (i.e., Essure), provided a hysterosalpingogram confirms success of the procedure at least 1 month before study Day 1
 - vasectomized partner, provided the vasectomized partner verbally confirms receipt of medical assessment of the surgical success and is the sole sexual partner of the female subject;
 - intrauterine device
 - Additional Effective Methods
 - male condom
 - diaphragm
 - cervical cap

or

- true abstinence which is defined as refraining from heterosexual intercourse if this is in line with the preferred and usual lifestyle of the subject (periodic abstinence [e.g., calendar, ovulation, symptothermal, postovulation methods] and withdrawal are not acceptable)

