There is an increased risk of venous thromboembolism in subjects with MM taking pomalidomide and dexamethasone; combined oral contraceptive pills are not recommended. If a subject is currently using combined oral contraception, the subject should switch to another highly effective method. The risk of venous thromboembolism continues for 4 to 6 weeks after discontinuing combined oral contraception. The efficacy of contraceptive steroids may be reduced during co-treatment with dexamethasone.

Implants and levonorgestrel-releasing intrauterine systems are associated with an increased risk of infection at the time of insertion and irregular vaginal bleeding. Prophylactic antibiotics should be considered, particularly in subjects with neutropenia.

For male subjects, pomalidomide is present in the semen of subjects receiving the drug. Therefore, male subjects must practice complete abstinence or always use a latex or synthetic condom during any sexual contact with females of reproductive potential while taking pomalidomide and for up to 4 weeks after discontinuing pomalidomide, even if they have undergone a successful vasectomy. Male subjects taking pomalidomide must not donate sperm during study participation and for up to 30 days after discontinuing any study drug.

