Deep venous thrombosis, pulmonary embolism, myocardial infarction, and stroke occur in subjects with multiple myeloma treated with pomalidomide. Antithrombotic prophylaxis is recommended for subjects with a history of cardiovascular disease or per investigator discretion. Refer to the pomalidomide package insert for details.¹⁰

Management of Infection

Subjects should receive anti-infective prophylaxis (e.g., amoxicillin/clavulanic acid or levofloxacin or equivalent per institutional guidelines) at least during the first 90 days of study and upon disease

progression for at least 30 days unless contraindicated per investigator discretion. Furthermore, subjects deemed at high risk of infection should receive immunoglobulin replacement therapy (i.e., IVIG) per institutional guidelines or at the investigator's discretion.

The use of antibiotics that are moderate or strong CYP3A inhibitors should be avoided or used with caution and with appropriate venetoclax dose modification (refer to [Appendix I](#)) as per protocol.

All subjects receiving venetoclax should be closely monitored for infections and in the event of a Grade ≥ 3 or serious infection, treatment with venetoclax should be interrupted and upon resolution, treatment can be either resumed at a reduced dose or discontinued, depending on investigator's clinical judgment.

Please refer to [Table 9](#) and [Table 10](#) for guidance on dose interruptions and/or reductions related to venetoclax toxicities.

Potential for drug-drug interactions should be considered. Please refer to [Appendix J](#) for a description of prohibited and cautionary medications.

Management of Other Toxicities

If other events occur that are related to venetoclax or pomalidomide, the investigator may interrupt or dose reduce venetoclax and/or pomalidomide, as appropriate (refer to [Appendix I](#)).

Pomalidomide must be permanently discontinued for angioedema, skin exfoliation, bullae, or any other severe dermatologic reaction.

All subjects should be monitored for new onset hematologic, hepatic, and renal toxicities with dose delay or reduction as appropriate. Please follow local, approved product label or applicable summary of product characteristics¹² for monitoring guidelines for pomalidomide or [Appendix I](#) for venetoclax.

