7.2 Determination of Sample Size

Approximately 60 subjects will be enrolled into this 2-part study.

Part 1, Dose Escalation

Part 1 will enroll approximately 3 to 6 subjects per cohort using a BOIN design, resulting in a total of 6 to 12 subjects.

Part 2, Dose Expansion

Part 2 will enroll approximately 50 subjects.

Arm A: t(11;14)-Positive

The historical ORR for pomalidomide + dexamethasone is 35%.^{13,14} By adding venetoclax to this combination, an ORR of 70% is clinically meaningful for t(11;14)-positive subjects. The sample size for Arm A will be approximately 23 subjects. Allowing for a maximum 1-sided type 1 error rate of 0.025 and assuming an ORR of 35% from the historical data, 23 subjects will provide 90% power if the true ORR for t(11;14)-positive subjects treated with venetoclax + pomalidomide + dexamethasone is 70%.

Arm B: t(11;14)-Negative

The historical ORR for pomalidomide + dexamethasone is 35%. By adding venetoclax to this combination, an ORR of 60% is clinically meaningful for t(11;14)-negative subjects. The sample size for Arm B will be approximately 27 subjects. Allowing for a maximum 1-sided type 1 error rate of 0.1 and assuming an ORR of 35% from the historical data, 27 subjects will provide 90% power if the true ORR for t(11;14)-negative subjects treated with venetoclax + pomalidomide + dexamethasone is 60%.

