Increase \geq 25% from baseline	
 • Start or increase rate of IV fluids. • Recheck potassium, phosphorus, uric acid, calcium, and creatinine in 1 to 2 hrs immediately.

ECG = electrocardiogram; IV = intravenous

APPENDIX I. RECOMMENDED DOSE REDUCTIONS RELATED TO DRUG TOXICITIES AND USE WITH CONCOMITANT MEDICATIONS

If a subject reports taking any over-the-counter or prescription medications, vitamins and/or herbal supplements or if administration of any medication becomes necessary from 30 days before the screening visit through 30 days after last dose of study drug, the name of the medication, dosage information including dose, route, and frequency, date(s) of administration including start and end dates, and reason for use must be recorded on the appropriate electronic Case Report Form (eCRF).

Subjects should receive full supportive care during study participation, including transfusion of blood products, fluid and electrolyte replacement, and antibiotics when appropriate. Subjects who use oral contraceptives, hormone-replacement therapy, or other maintenance therapy should continue their use. For guidance regarding medications for management of tumor lysis syndrome (TLS) and neutropenia, refer to Section 6.4.

General guidelines regarding prohibited, cautionary, and allowed medications are summarized in Section 5.3 and Section 5.4. A sample list of prohibited and cautionary medications that may interact with study drugs is provided in [Appendix J](#). It is not possible to produce a complete list of medications that fall into these categories; if in question, please refer to the appropriate product label.

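### Appendix I tells oral-contraceptive users to continue without exception, while Section 5.2 tells combined-pill users to switch because of thromboembolism risk

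*Protocol*

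**What the plan says.** Protocol Appendix I covers dose reductions and concomitant medication. In its general paragraph on supportive care it states: "Subjects who use oral contraceptives, hormone-replacement therapy, or other maintenance therapy should continue their use". The sentence does not distinguish combined from progesterone-only pills.

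Protocol Section 5.2, the contraception section, addresses the combined pill directly: "There is an increased risk of venous thromboembolism in subjects with MM taking pomalidomide and dexamethasone; combined oral contraceptive pills are not recommended". The next sentence gives the action: "If a subject is currently using combined oral contraception, the subject should switch to another highly effective method". Section 5.2 adds that the thromboembolism risk persists for 4 to 6 weeks after a combined pill is stopped. Its list of highly effective methods names birth control pills in general and also, specifically, a progesterone-only pill that inhibits ovulation.

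For further medication guidance Appendix I sends the reader elsewhere: "General guidelines regarding prohibited, cautionary, and allowed medications are summarized in Section 5.3 and Section 5.4". It also cites Section 6.4 (for tumor lysis syndrome and neutropenia), Appendix J and the product labels. It does not cite Section 5.2.

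**The concern.** A combined-pill user receives two opposite instructions: continue (Appendix I) and switch (Section 5.2). Section 5.2 gives a safety reason that applies to every subject, since all are assigned pomalidomide and dexamethasone. By the protocol's own reasoning, Appendix I is therefore the less safe text. A site that uses Appendix I as its concomitant-medication reference would keep a subject on a pill that the protocol elsewhere says to replace.

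Possible harms are serious. The thromboembolism paragraph of Section 6.4 lists deep venous thrombosis, pulmonary embolism, myocardial infarction and stroke among events seen with pomalidomide. A late correction would not protect at once, given the 4 to 6 weeks of residual risk stated in Section 5.2.

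**Working it through.** No figure in the plan needs to be reproduced. The check compares texts, followed by a bound on the number of subjects.

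**1. Are both instructions current?** Yes. Both stand in the body of the protocol and its working appendices, not in the Appendix M summary of changes.

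**2. Do they address the same subject?**

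| Subject at entry | Section 5.2 | Appendix I | Compatible? |
|---|---|---|---|
| Combined-pill user | Not recommended; switch | Continue | No |
| Progesterone-only pill user | Accepted as highly effective | Continue | Yes |
| Hormone-replacement user | Not addressed | Continue | Yes |

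The conflict is confined to the first row.

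**3. Does any place that Appendix I cites resolve it?**

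- Section 5.3 lists CYP3A and CYP1A2 inhibitors and CYP3A inducers, and points back to the concomitant-medication criteria in Section 5.1. Neither mentions oral contraceptives.
- Section 5.4 (cautionary and allowed medication, supportive care) does not mention them.
- Section 6.4 (toxicity management) does not mention them.
- Appendix J (sample list of interacting drugs) does not mention them.

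A reader who starts in Appendix I and follows its protocol cross-references does not reach the switch instruction.

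**4. Does thromboprophylaxis cover the gap?** Not reliably. Section 6.4 says: "Antithrombotic prophylaxis is recommended for subjects with a history of cardiovascular disease or per investigator discretion". Section 5.4 lists daily low-dose aspirin, or low molecular weight heparin, among supportive care that may be needed, and ties this to prior thrombotic disease and local practice. The wording leaves unclear whether the history condition applies to aspirin as well as heparin. Neither section requires prophylaxis for every subject, so a combined-pill user without such a history has no assured cover.

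**5. How many subjects could be concerned?** Section 7.2 gives the total: "Approximately 60 subjects will be enrolled into this 2-part study". By part:

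- lower end: 6 (Part 1) + 50 (Part 2) = 56
- upper end: 12 (Part 1) + 50 (Part 2) = 62

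The documents give no share of combined-pill users. It should be low, because Section 2.1 says of multiple myeloma: "It is the most prevalent hematologic malignancy in patients older than 65 years of age". Taking 0% to 2% as an assumption:

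- lower bound: 62 × 0 = 0
- upper bound: 62 × 0.02 = 1.24, or about 1 subject

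This counts users, not subjects misdirected. If *q* is the fraction of users whose site follows Appendix I instead of Section 5.2, the number misdirected is at most 1.24 × *q*, with *q* between 0 and 1. The documents give no value for *q*.

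**The case against.** The strongest reply is that Section 5.2 governs. It is the dedicated section, it treats this exact case, it says that its guidelines must be followed, and eligibility criterion 21 sends sites to it before the first dose. On that reading, the Appendix I sentence is a general supportive-care line that applies after entry, when users of combined pills have already changed method, and continuing means staying on compliant contraception.

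The opposition is also softer than a breached prohibition. Section 5.2 advises against combined pills without banning them, both texts use *should*, and Section 5.2 itself lists birth control pills in general among acceptable methods. A site in doubt could consult the product label or the sponsor's medical director.

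Much of this stands, and it lowers the exposure: most users should have switched at entry, so the expected number misdirected is below the bound of about 1. It does not remove the conflict. Appendix I neither states that Section 5.2 has been applied nor refers to it. Reading the two texts together works only for someone who already knows Section 5.2, and asking for advice requires a doubt that Appendix I gives no reason to have. The generic mention of birth control pills in Section 5.2 is qualified by its later paragraph on combined pills.

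**Conclusion.** The concern holds. For combined-pill users the protocol gives two opposite current instructions, and the one in Appendix I is the less safe on the protocol's own reasoning. This is an error in the text as written, not a missing detail.

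Its practical size is very small: at most about 1 of 56 to 62 subjects, under the assumption that 0% to 2% take a combined pill, and fewer to the extent that sites apply Section 5.2 at screening. It has no bearing on sample size, error rates, endpoints or analysis. It should be corrected because the possible harm is serious and the correction is trivial, but it does not justify a stand-alone amendment.

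**What to change.** Keep the Appendix I sentence, including its instruction on hormone-replacement and other maintenance therapy, and add at its end:

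> *except combined oral contraceptives, which should be switched to another highly effective method per Section 5.2*

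This also supplies the missing cross-reference. The cost is one clause in the next amendment, with no new procedures, visits or data collection.

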Investigators:	Investigator information on file at AbbVie.
Study Sites:	Approximately 15 sites in approximately 3 countries
Study Population and Number of Subjects to be Enrolled:	The patient population consists of subjects with R/R MM. The study will enroll approximately 6 to 12 subjects in the dose-escalation phase (Part 1) and approximately 50 subjects in an expansion phase (Part 2).
Investigational Plan:	
This is an open-label, multicenter study designed to evaluate the safety and preliminary efficacy of venetoclax combined with pomalidomide and dexamethasone in subjects with R/R MM who have received at least 1 prior line of therapy. The study will consist of 2 parts: Part 1 (dose escalation) and Part 2 (dose expansion).
 
The dose-escalation phase of the study will evaluate the safety, tolerability, and PK profile of combination therapy with venetoclax, pomalidomide, and dexamethasone in 6 to 12 subjects who will be enrolled in 2 cohorts of at least 3 subjects per cohort. In the first cohort, a low dose of venetoclax (400 mg oral [PO], once daily [QD]) will be administered with the approved dose of pomalidomide (4 mg PO, QD) and dexamethasone (40 mg once weekly [qw]). If acceptable safety and tolerability are observed at the completion of Cycle 1 with at least 3 dose-limiting toxicity (DLT)-evaluable subjects, the dose of venetoclax will be escalated to 800 mg QD, which has been identified as the target dose; the dose of pomalidomide and dexamethasone will not change. The decision to escalate to the higher dose of venetoclax will be made according to the Bayesian optimal interval (BOIN) design and based on

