4 INVESTIGATIONAL PLAN

4.1 Overall Study Design and Plan

The schematic of the study is shown in [Figure 1](#). Further details regarding study procedures are located in [Appendix E](#).

This is an open-label, multicenter study designed to evaluate the safety and preliminary efficacy of venetoclax combined with pomalidomide and dexamethasone in subjects with R/R MM who have received at least 1 prior line of therapy. The study will consist of 2 parts: Part 1 (dose escalation) and Part 2 (dose expansion).

Part 1: Dose Escalation

The dose-escalation phase of the study will evaluate the safety, tolerability, and PK profile of combination therapy with venetoclax, pomalidomide, and dexamethasone in 6 to 12 subjects who will be enrolled in 2 cohorts of at least 3 subjects per cohort. In the first cohort, a low dose of venetoclax (400 mg oral [PO], once daily [QD]) will be administered with the approved dose of pomalidomide (4 mg PO, QD) and dexamethasone (40 mg once weekly [qw]). If acceptable safety and tolerability are observed at the completion of Cycle 1 with at least 3 dose-limiting toxicity (DLT)-evaluable subjects, the dose of venetoclax will be escalated to 800 mg QD (Cohort 2), which has been identified as the target dose; the dose of pomalidomide and dexamethasone will not change. The decision to escalate to the higher dose of venetoclax will be made according to the Bayesian optimal interval (BOIN) design and based on the cumulative number of subjects who experience a DLT at the current combination dose.

Table 1 displays the dose-escalation decision rule for the BOIN design with target toxicity rate of 30% and optimal interval of (23.6%, 35.9%).

Table 1. Dose-Escalation Decision Rule

Action	Number of DLT-Evaluable Subjects Treated at Current Combination							
	3	4	5	6	7	8	9	10
Escalate if number of subjects with DLT ≤	0	0	1	1	1	1	2	2
Stay at current combination if number of subjects with DLT =	1	1	-	2	2	2	3	3
De-escalate if number of subjects with DLT ≥	2	2	2	3	3	3	4	4
Eliminate ^a if number of subjects with DLT ≥	3	3	4	4	5	5	5	6

DLT = dose-limiting toxicity

a. Eliminate current combination and higher combinations (i.e., venetoclax dose and pomalidomide dose ≥ current dose level).

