Concomitant administration of moderate or strong cytochrome P450 (CYP)3A and strong CYP1A2 inhibitors is prohibited during Part 1 (dose escalation), Cycle 1. Use of strong or moderate CYP3A inhibitors and strong CYP1A2 inhibitors is allowed (with appropriate venetoclax and pomalidomide dose reductions, respectively) after Part 1 (dose escalation), Cycle 1 and throughout the study for subjects enrolled in Part 2 (dose expansion) if no appropriate therapeutic alternative exists. Venetoclax dose reductions for concomitant administration with moderate or strong CYP3A inhibitors are presented in [Table 7](#). Subjects should be monitored more closely for signs of toxicities and the venetoclax dose may need to be further reduced. Pomalidomide dose reductions for concomitant use with strong CYP1A2 inhibitors are presented in [Table 8](#). Subjects should be monitored more closely for signs of toxicities and the venetoclax dose may need to be further reduced. After discontinuation of the CYP3A inhibitor, wait for 3 days before venetoclax dose is increased back to the target dose.

Concomitant administration of moderate or strong CYP3A inducers is prohibited during Cycle 1 (dose escalation), Part 1. After completion of Cycle 1 (dose escalation), Part 1, and throughout the study for subjects enrolled in Part 2 (dose expansion), concomitant use of moderate or strong CYP3A inducers should still be avoided. Alternative treatments with less CYP3A induction should be considered.

Study drug dose levels are presented in [Table 9](#). Toxicities related to venetoclax, pomalidomide, and dexamethasone are presented in [Table 10](#), [Table 11](#), and [Table 12](#), respectively.

Table 7. Dose Modifications for Venetoclax with Concomitant Moderate and Strong CYP3A Inhibitor Use

Venetoclax Dose with No Moderate or Strong CYP3A Inhibitor	Venetoclax Dose if Co-Administered with a Moderate CYP3A Inhibitor	Venetoclax Dose if Co-Administered with a Strong CYP3A Inhibitor
400 mg	200 mg	100 mg
600 mg	300 mg	100 mg
800 mg	400 mg	200 mg

CYP = cytochrome P450

Table 8. Dose Modifications for Pomalidomide with Concomitant Strong CYP1A2 Inhibitor Use

Assigned Pomalidomide Dose	Pomalidomide Dose if Co-Administered with a Strong CYP1A2 Inhibitor
4 mg	2 mg

CYP = cytochrome P450

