The AbbVie Therapeutic Area Medical Director (TA MD) identified in [Appendix L](#) should be contacted if there are any questions regarding concomitant or prior therapy(ies) and venetoclax or pomalidomide dose reductions.

Table 9. Study Drug Dose Levels

Dose	Venetoclax	Pomalidomide	Dexamethasone (< 75 years of age)	Dexamethasone (≥ 75 years of age)
Starting dose	800 mg	4 mg	40 mg	20 mg
Dose level –1	600 mg	3 mg	20 mg	12 mg
Dose level –2	400 mg	2 mg	12 mg	8 mg
Dose level –3	200 mg	1 mg	8 mg	4 mg

Table 10. Toxicities Related to Venetoclax

Toxicities	Recommended Action
Grade 3 or Grade 4 neutropenia with infection or fever; or Grade 4 hematologic toxicities (except for lymphopenia)	
 • G-CSF or growth factors for neutropenia should be administered with venetoclax if clinically indicated. • For Grade 4 neutropenia (ANC < 500 cells/μL) without infection, anti-infective prophylaxis (e.g., amoxicillin/clavulanic acid or levofloxacin or equivalent per institutional guidelines) is recommended until the neutropenia improves to Grade 3 or better (ANC > 500 cells/μL). • First episode: Interrupt venetoclax and once the toxicity has resolved to Grade 1 or baseline level, venetoclax may be resumed at the same dose. • For subsequent episodes: Interrupt venetoclax. Consider using G-CSF as clinically indicated. Follow dose reduction guidelines when resuming treatment with venetoclax after resolution. A larger dose reduction may occur at the discretion of the investigator and according to the dose reduction guidelines.
Grade \geq 3 or serious infections	
 • Interrupt venetoclax and upon resolution, treatment can either be resumed at a reduced dose (see Table 9) or discontinued, at the discretion of the investigator.
Grade 3 or 4 non-hematologic events	
 • First episode: Interrupt venetoclax. Once toxicity has resolved to Grade \leq 1 or baseline, venetoclax may be resumed at the same dose. No dose modification is required. • For subsequent episodes: Interrupt venetoclax. Follow dose reduction guidelines when resuming treatment with venetoclax after resolution. A larger dose reduction may occur at the discretion of the investigator and according to the dose reduction guidelines.

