
Warfarin**
 
P-gp substrates – aliskiren, ambrisentan, colchicine, dabigatran etexilate, digoxin, everolimus,* fexofenadine, lapatinib,* loperamide, maraviroc, nilotinib,* ranolazine, saxagliptin, sirolimus,* sitagliptin, talinolol, tolvaptan, toptecan*
 
BCRP substrates – methotrexate,* mitoxantrone,* irinotecan,* lapatinib,* rosuvastatin, sulfasalazine, toptecan*
 
OATP1B1/1B3 substrates – atrasentan, atorvastatin, ezetimibe, fluvastatin, glyburide, rosuvastatin, pitavastatin, pravastatin, repaglinide, simvastatin acid, telmisartan, valsartan, olmesartan
 
P-gp inhibitors – amiodarone, azithromycin, captopril, carvedilol, dronedarone, felodipine, quercetin, quinidine, ronalzine, ticagrelor
 
BCRP inhibitors – gefitinib*
 
Corticosteroids – cortisone, hydrocortisone, methylprednisolone, prednisolone, prednisone, triamcinolone, betamethasone, dexamethasone

BCRP = breast cancer resistance protein; CYP = cytochrome P450; FDA = Food and Drug Administration; OATP = organic anion-transporting polypeptide; P-gp = P-glycoprotein; USPI = United States package insert

a. Moderate CYP3A inhibitor per venetoclax FDA USPI.

* These are anticancer agents; contact the AbbVie Therapeutic Area Medical Director before use.

** Closely monitor the international normalized ratio.

† If a subject requires use of these medications, use with caution and reduce the venetoclax dose by 75%. After discontinuation of the CYP3A inhibitor, wait for 3 days before venetoclax dose is increased back to the target dose.

‡ If subject requires use of these medications, use with caution and reduce the venetoclax dose by 50%. After discontinuation of CYP3A inhibitor, wait for 3 days before venetoclax dose is increased back to the target dose.

†† If a subject requires use of these medications, use with caution and reduce the pomalidomide dose by 50%.

Note: this is not an exhaustive list. For an updated list, see the following link:

<http://www.fda.gov/Drugs/DevelopmentApprovalProcess/DevelopmentResources/DrugInteractionsLabeling/ucm093664.htm>

In addition to the medications listed in this table, subjects receiving venetoclax should not consume grapefruit, grapefruit products, Seville oranges (including marmalade containing Seville oranges), or Star fruits. Herbal and natural remedies are to be avoided.

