#### 4.2 Study Design and Design Diagram

[figure not shown]
This is an open-label, multicenter study with two phases, diagrammed in [Figure 1](#).

1. **Dose escalation** will consider 6 – 12 subjects confirmed to be t(11;14)+ by an analytically-validated FISH assay per central laboratory testing before enrollment. Dose escalation will be guided by a Bayesian optimal interval (BOIN) design, based on the cumulative number of subjects who experience a DLT at the current combination dose. The subjects will be enrolled in cohorts of at least 3 subjects. The first cohort will be administered a 400 mg dose of venetoclax orally, once daily (QD). If acceptable safety and tolerability are observed at the completion of Cycle 1 in at least 3 DLT-evaluable subjects, the dose of venetoclax will be

escalated to 800 mg QD (the target dose). All subjects will be administered the approved dose of pomalidomide (oral 4 mg QD) and dexamethasone (40 mg once weekly (qw)). To be considered DLT-evaluable, subjects must complete at least 80% of pomalidomide and venetoclax dosing (or experience a DLT) during Cycle 1. DLTs are defined in the operations manual. Additional information regarding the BOIN design is provided in [Appendix A](#).

2. **Dose expansion** will consist of 2 independent arms. Arm A will consider t(11;14)+ subjects, and Arm B will consider non-t(11;14) subjects. All subjects who participate in this phase must be screened for t(11;14) translocation status before enrollment. Arm A will feature around 23 subjects and Arm B will feature around 27 subjects. All subjects will receive the ven/pom/dex combination until documented PD, unacceptable toxicity, withdrawal of consent, or they meet another criteria for discontinuation (see study protocol). Subjects may discontinue pomalidomide but continue receiving venetoclax QD for up to 2 years following the date of the last subject enrolled, provided they completed Cycle 1 of ven/pom/dex, continue to tolerate venetoclax, do not exhibit PD, and do not meet any criteria for discontinuation. AbbVie will work with the investigator to evaluate options for continued venetoclax therapy for subjects that continue to derive benefit after 2 years of treatment.

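### The rule for raising venetoclax after a CYP3A inhibitor stops names the target dose, a term the documents tie only to 800 mg, so it does not fit subjects whose own dose is lower

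*Protocol*

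**What the plan says.** After Cycle 1 of Part 1, and throughout Part 2, moderate and strong CYP3A inhibitors may be used with a lowered venetoclax dose if there is no suitable alternative (Protocol Section 5.4 and Appendix I). Table 7 gives the lowered dose. Its left column is headed "Venetoclax Dose with No Moderate or Strong CYP3A Inhibitor" and has rows for 400, 600 and 800 mg.

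For the return to full dosing, Appendix I says: "After discontinuation of the CYP3A inhibitor, wait for 3 days before venetoclax dose is increased back to the target dose". In Appendix J, the footnote for strong inhibitors and the footnote for moderate inhibitors both end with the same instruction: "wait for 3 days before venetoclax dose is increased back to the target dose".

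The term gets a value in three places, always the same one:

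- Synopsis, Investigational Plan: "the dose of venetoclax will be escalated to 800 mg QD, which has been identified as the target dose".
- Protocol Section 4.1: "the dose of venetoclax will be escalated to 800 mg QD (Cohort 2), which has been identified as the target dose".
- SAP Section 4.2 also attaches the term to 800 mg once daily.

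Table 9 sets the venetoclax reduction levels at 600, 400 and 200 mg. Table 10 calls for reductions after events such as a Grade 3 or higher or serious infection (if venetoclax is resumed), repeat episodes of severe toxicity, or clinical tumor lysis syndrome. The Synopsis assigns 400 mg to Part 1 Cohort 1.

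**The concern.** The return instruction is an operative dosing rule, and sites will apply it. It names its end point by a term that elsewhere means only 800 mg, and it makes no exception for a subject whose dose was below 800 mg before the inhibitor began. For that subject the rule, taken at its word, sets the wrong dose.

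The overlap is foreseeable. Section 6.4 has venetoclax interrupted for a Grade 3 or higher or serious infection and then either resumed at a lower dose or stopped. The same section anticipates antibiotics that inhibit CYP3A, and Appendix J lists anti-infectives such as clarithromycin, voriconazole, fluconazole and erythromycin. One infection can therefore bring both a toxicity reduction and an inhibitor. Section 2.2 says the infection guidance was added after the BELLINI analysis. What is at stake is that a reduction made for safety could be lost by accident when the inhibitor stops.

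**Working it through.** The check is a reading of the term, followed by simple ratios. The plan gives no figure to reproduce.

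**Step 1. Uses of the term.** *Target dose* occurs six times in the two documents.

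| Place | Value given |
|---|---|
| Protocol Synopsis, Investigational Plan | 800 mg |
| Protocol Section 4.1 | 800 mg |
| SAP Section 4.2 | 800 mg |
| Appendix I, return instruction | none |
| Appendix J, strong-inhibitor footnote | none |
| Appendix J, moderate-inhibitor footnote | none |

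The return instructions neither give a value nor redefine the term. Where the protocol discusses re-escalation after tumor lysis syndrome (Sections 6.4 and 6.5), it uses other expressions for the dose to be regained.

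**Step 2. Whom the rule covers.** Table 7 has rows for 400 and 600 mg, so subjects below 800 mg are expected to use the inhibitor rules. They get there by toxicity reduction (Tables 9 and 10) or by assignment to Cohort 1.

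**Step 3. Size under the literal reading.** Ratio = literal return dose / correct return dose, with the literal dose 800 mg and the correct dose the subject's own inhibitor-free dose.

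| Subject's own dose | Source | Ratio |
|---|---|---|
| 600 mg | Table 9, level -1 | 800/600 = 1.33 |
| 400 mg | Table 9, level -2, or Cohort 1 | 800/400 = 2 |
| 200 mg | Table 9, level -3 | 800/200 = 4 |
| 800 mg | starting dose | 800/800 = 1 (no error) |

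**Step 4. Whether Table 7 settles the dose.** Read forwards, from a known inhibitor-free dose, it does so for 400, 600 and 800 mg. Read backwards it is ambiguous: 100 mg with a strong inhibitor corresponds to both 400 and 600 mg. The 200 mg level has no row. The return dose therefore has to come from the subject's dosing record.

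**Step 5. Toxicity during inhibitor use.** Appendix I says: "Subjects should be monitored more closely for signs of toxicities and the venetoclax dose may need to be further reduced". The return instruction follows without saying what happens to such a further reduction. The Table 9 levels do not answer this directly: a subject on 800 mg takes 200 mg with a strong inhibitor, so a further cut from there is not one of the steps from 800 to 600, 400 or 200 mg.

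**The case against.** The best case for the existing text is that its meaning is clear in context. Something is raised *back* only to where it was. The sentence reverses a reduction made for an inhibitor, and Table 7 in the same appendix starts from the subject's inhibitor-free dose. A site that used the 600 mg row to lower the dose knows which dose to restore. *Target dose* is also not listed as a defined term in Appendix A; the Synopsis and Section 4.1 use it to describe where Part 1 escalation is heading. This stands as the likely intent.

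There are safeguards too. Section 6.5 caps venetoclax at the highest tolerated dose level, and Appendix I names the sponsor's medical director, who "should be contacted if there are any questions regarding concomitant or prior therapy(ies) and venetoclax or pomalidomide dose reductions". Both lessen the risk. But the cap sits in the dose-limiting toxicity section and does not say whether the level is the subject's or the cohort's. The contact helps only a site that sees a question to ask, and a site that takes the term to mean 800 mg may see none.

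A reader might infer that the protocol deliberately orders toxicity reductions to be undone. The documents do not support that: written provisions for raising the dose after toxicity appear only for tumor lysis syndrome and dose-limiting toxicities, with a risk assessment, a discussion with the medical director, or both.

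A reader might also measure the problem by the jump from the inhibitor-lowered dose, for example 100 to 800 mg, or 8-fold. That jump includes the intended restoration and compares doses taken with and without CYP3A inhibition. Only 1.33, 2 and 4 measure the error.

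**Conclusion.** The point holds as a wording defect. The three return instructions use a term tied only to 800 mg, and for a subject properly on 600, 400 or 200 mg the literal result is 1.33, 2 or 4 times the correct dose. This rests on two assumptions: that a site follows the sentence as written and does not infer the intent from *back* and Table 7, and that neither the Section 6.5 cap nor a call to the medical director intervenes.

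The documents give no basis for estimating how often such a subject would stop an inhibitor, how often the sentence would be read literally, or what harm would follow. The BELLINI deaths do not size it: that trial used a different combination, and the account in Section 2.1 links no death to venetoclax dose or to CYP3A inhibitor use.

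It might also seem to follow that every reduction made during inhibitor use must persist afterwards. The documents do not settle that. Toxicity at that time may reflect raised exposure that ends with the inhibitor, so it is a clinical judgment.

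The point is minor and does not affect the endpoints, the sample size, the response-rate tests or any other analysis.

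**What to change.** At all three places (the Appendix I sentence and both CYP3A footnotes in Appendix J), replace *the target dose* with *the venetoclax dose the subject was receiving immediately before the CYP3A inhibitor was started*, and say that this dose is taken from the dosing record.

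Add one sentence: if venetoclax was further reduced for toxicity while the inhibitor was in use, the investigator decides the return dose with the sponsor's medical director. This also covers a subject whose venetoclax is interrupted for an infection and resumed at a lower dose while an inhibitor is being given.

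The cost is one replaced phrase at three places and one added sentence, which could go into the next amendment. No new data collection is needed, and the SAP does not change.
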